a “woman” word [e.g., female] or an “object” word [e.g., tool] appears on the screen vs. pressing “e” whenever a “woman” word or a “human” word [e.g., person] appears). Making a response is easier (and thus faster) when closely related constructs share the same response key. Therefore, quicker response times when woman and object (vs. human) words are paired represents more implicit objectification. We expect intoxication to cause faster reaction times when women and object words are paired and slower reaction times for pairings of women and human words.

The Other-Objectification Questionnaire (modified from Grabe, Rutledge, Cook, Andersen, & Arndt, 2005; Curran, 2005), which assesses the frequency (6=very frequently, 1=never) with which the male participant objectified the female confederate (e.g., I focused more on her body than our conversation). Scores are averaged with higher scores representing more objectification of women. We expect intoxication to cause more weight to be placed on women’s objectifying compared to human attributes in men’s evaluations.

Sexual aggression. To assess sexual aggression, participants will complete the Laboratory Analogue of Sexual Aggression (Parrott et al., 2012) based on Hall, Hirschman, and Olivier (1994). Following the ostensible interaction in which the participant learns that the female participant dislikes media with sexual content, men then select one clip—containing either a man and a woman having sexual intercourse or a similar clip without sexual content—for the woman to watch based on still shots and synopses. Choosing the sexual (vs. non-sexual) clip represents sexual aggression. Although perpetrators may justify their choices (e.g., reasoning that the woman may not like sexual content in general, but that she would like this sexual content in particular), such responses fall under the CDC definition of sexual violence (i.e., subjecting a woman to an unwanted sexual experience). Validity of the paradigm is supported by expected positive associations between selection of the sex video and self-reported history of sexual aggression perpetration, adversarial heterosexual beliefs, hostility toward women, and hostile sexism (Parrott et al., 2012). We expect intoxication to cause more sexual aggression.

Study 2: Self-Objectification and Alcohol-Involved Sexual Victimization (Aim 2)

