Risk for sexual victimization. Due to the ethical proscriptions against replicating sexual victimization in the lab, we will assess risk for victimization using the Risk Perception Survey (RPS; Messman-Moore & Brown, 2006). The RPS consists of vignettes depicting forced sexual intercourse. The vignettes include clear (sexual comments, male persistence) and ambiguous (alcohol consumption, physical isolation) risk factors. They contain chronological statements that become progressively riskier as the man increases his coercion. Respondents imagine themselves interacting with the man and the RPS yields a "leave" variable, which reflects the point at which the participant indicates she would leave. We expect impaired risk perception as indicated by higher "leave" values when women are intoxicated and objectified.

Objectification and Alcohol-Involved Sexual Assault: Critical Moderators (Aim 3).

To address Aim 3, participants in Study 1 and Study 2 will complete measures of key moderators online prior to coming to the lab. In Study 1 men will complete the 10-item Sexual Experiences Survey-Short Form Perpetration (SES-SFP; Koss et al., 2007). The SES-SFP assesses the frequency (0 to 3+) of unwanted sexual contact, coercion, attempted rape, and rape. Men will also complete the 10-item Other-Objectification Questionnaire (OOQ) in which

they will rank order the importance of 10 objectifying attributes (e.g., sex appeal) and humanizing, internal attributes to assess overall objectification of women (Noll & Fredrickson, 1998; Grabe et al., 2005; e.g., relative importance of sex appeal vs. well-being, internal states, attributes in women). The ranking for the human attributes is subtracted from the ranking of the objectifying attributes with higher numbers indicating greater objectification of women.

Women in Study 2 will complete the 10-item Self-Objectification Questionnaire (SOQ; Noll & Fredrickson, 1998) that uses the same items, response format, and scoring procedure as the OQ, except people are asked to rank the objectifying and human attributes in themselves to assess self-objectification. Sexual victimization will be assessed with the 10-item Sexual Experiences Survey-Short Form Victimization; SES-SFV; Koss et al., 2007), which assesses the frequency of unwanted sexual advances using the same format as the SES-SFP, but with items worded for victimization rather than perpetration.

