Both men and women will complete the 18-item Sex-Related Alcohol Expectancies Scale (SRAES, Dermen & Cooper, 1994), that assesses the degree to which people associate alcohol consumption with sexual disinhibition and risk (e.g., I have sex with people whom I wouldn't have sex with if I were sober) on 6-point scales (1 = strongly disagree, 6 = strongly agree). The SRAES is psychometrically sound including adequate internal consistency reliability ($\alpha = .70 - .83$) and is correlated with alcohol use and sexual risk-taking (Dermen & Cooper, 1994). Men and women will also complete the 19-item Rape Myth Acceptance Scale (RMAS, Burt, 1980), which assesses people's support of rape myths (e.g., Any healthy woman can successfully resist a rapist if she really wants to) on 7-point scales (1 = strongly disagree, 7 = strongly agree).

We expect the predicted effects to be most pronounced for men high on objectification and with a history of sexual assault perpetration (Study 1) and for women high on self-objectification and with a history of sexual assault victimization (Study 2). We also expect these effects to be more exaggerated for men (Study 1) and women (Study 2) high in sex-related alcohol expectancies and rape myth acceptance.

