Since the majority of the moderation hypotheses for Aim 3 involve manifest, continuous variables, moderation will be tested using the conditional process model framework (Hayes, 2013) rather than multi-group structural equation methods. The conditional process model framework involves taking the mediation models from Aims 1 and 2, and adding the two-way interactions between measures of myopia (impaired attentional capacity and sexual and self-objectification) and the moderators. We hypothesize, (a) prior objectification of women by men and (b) self-objectification in women to moderate the relation between impaired attention and situational sexual and self-objectification. Specifically, we expect impaired attention to predict sexual objectification in men, but these effects should be particularly pronounced for men who chronically objectify women. Likewise, we expect impaired attention to predict self-objectification in women, but that these effects should be particularly pronounced for women who chronically self-objectify. We also expect histories of sexual assault perpetration (men), or

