sexual victimization history (women), as well as, sex-related alcohol expectancies and rape myth acceptance to emerge as significant moderators of the relation between objectification and assault. Specifically, we expect sexual objectification to predict sexual aggression perpetration in men and self-objectification to predict victimization risk in women, but these effects should be particularly pronounced for people with a history of sexual assault (perpetration in men, victimization in women), as well as for people who endorse more rape myths and those who hold higher sex-alcohol expectancies. All continuous variables (i.e., all variables except the dichotomous measure of aggression in Study 1) will be grand mean centered prior to creating the interaction terms to improve interpretability as recommended by Cohen, Cohen, West, and Aiken (2003). The process will then be repeated for the measures of objectification and the moderator variables. Given the correlations between the moderator variables, the two-way interactions will be examined individually first. All significant interactions will be added to the model simultaneously to examine whether moderation remains. Type I error inflation across models will be controlled for using the Scheffe correction and no effects that explain less than 1% of the total variance will be considered important, regardless of statistical significance.

Missing data. Because the proposed studies are lab experiments, large amounts of missing data are unexpected. Data missing due to equipment malfunctions are missing completely at random (MCAR) and data missing due to nonresponses from participants will be considered missing at random (MAR). The methods for dealing with MCAR and MAR data are full information maximum likelihood (FIML) and multiple imputation (Enders, 2010). By default, Mplus uses FIML, so FIML will be used here for all analyses. Also, bias analyses will be conducted to examine demographics of people who participated in our study compared to people who were recruited for the study, but did not meet the inclusion criteria or who did not agree to participate in our study.

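### Aim 3 tests moderation only on the mediator paths, so the protocol's prediction about the randomised conditions is tested only in part, and some moderation can be credited to the wrong path

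*SAP*

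**What the plan says.** **Protocol.** The expectations stated for each measure in Studies 1 and 2 are effects of the randomised conditions on attention, gaze, implicit and self-reported objectification, aggression and risk perception. For aggression: "We expect intoxication to cause more sexual aggression". The Critical Moderators (Aim 3) section then says "We expect the predicted effects to be most pronounced for men high on objectification and with a history of sexual assault perpetration", makes the parallel statement for women, and continues: "We also expect these effects to be more exaggerated for men (Study 1) and women (Study 2) high in sex-related alcohol expectancies", with rape myth acceptance named alongside. The moderators are measured online before the lab visit.

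**SAP, Aim 3 paragraphs.** The mediation models are extended by "adding the two-way interactions between measures of myopia (impaired attentional capacity and sexual and self-objectification) and the moderators". Chronic objectification and self-objectification are expected "to moderate the relation between impaired attention and situational sexual and self-objectification". Assault history, alcohol expectancies and rape myth acceptance are expected "to emerge as significant moderators of the relation between objectification and assault". A second round repeats the process with the objectification measures. Condition enters as a main effect, with alcohol × gaze added in Study 2. No condition × moderator term is listed for any outcome. The power section says that its Aim 3 calculation corresponds to moderation of the objectification–outcome path.

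**The concern.** The protocol's wording refers back to effects of randomised factors, and it states no separate expectation for a path from attention to objectification or from objectification to aggression. A randomised condition crossed with a baseline moderator gives a protected answer to the question of for whom alcohol raises aggression or risk. Mediator × moderator terms are not randomised and answer a different question.

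The omission also affects the terms that are fitted. Under H1b and H2b condition shifts the mediators, so mediator × moderator is correlated with condition × moderator. With the second left out, the first absorbs part of its effect, and the report may say that a moderator works through objectification when it acts on the alcohol effect by another route.

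**Working it through.** **1. Prediction against planned test**

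| Effect that the moderators should enlarge | Test in the SAP |
|---|---|
| Condition on aggression or risk, total | None |
| Condition on aggression or risk, direct | None |
| Condition on attention, and on objectification | None |
| Condition on outcome through the mediators | Implied by a moderated mediator path; no test of a conditional indirect effect is named |

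The SAP's option to run mediation in each of the four Study 2 groups splits by condition, not by baseline moderator.

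**2. The plan's own figures.** For one tested term, noncentral F with λ = N·f², two-sided .05 (assumed; the SAP gives no alpha) and power .80:
- N=150 gives f² = .0530, matching the stated .053.
- N=210 gives f² = .0377, not the stated .044. The stated figure is conservative, with power .857 at .044. Both values are carried below.

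**3. Inputs**
- Condition–mediator path *a*: .26 and .39 are the SAP's planning coefficients. Its statement that alcohol explains 10% of objectification variance gives √.10 = .316.
- Condition × moderator effect: f² = .02 (the SAP's small effect), .053, .0377 and .044.
- Assumed: true mediator × moderator effect of zero, and no Scheffé correction yet.

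**4. Mechanism, linear outcome.** Let X = ±1, M = aX + e with variance 1, W an independent standard normal moderator, and c the coefficient of X·W. Since E[(XW)(MW)] = a and Var(MW) = 1, leaving out X·W gives M·W an expected coefficient of a·c although its true value is zero. The test statistic is then centred near

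δ = a·√[N·f² / (1 + f²(1 − a²))].

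Example, N=150, f²=.053, a=.316: N·f² = 7.95; 1 + .053 × .90 = 1.048; √(7.95/1.048) = 2.755; δ = .316 × 2.755 = .87. Then P(|Z + .87| > 1.96) = .140.

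| N | f² | a=.26 | a=.316 | a=.39 |
|---|---|---|---|---|
| 150 | .02 | 7.3% | 8.4% | 10.3% |
| 150 | .053 | 11.0% | 14.0% | 18.9% |
| 210 | .02 | 8.2% | 9.8% | 12.4% |
| 210 | .0377 | 11.1% | 14.1% | 19.1% |
| 210 | .044 | 12.1% | 15.6% | 21.4% |

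Simulation of the same set-up agrees to within one or two percentage points: about 8–13% at f²=.02, 11–19% at f²=.053 (N=150), 11–19% at f²=.0377 and 12–22% at f²=.044 (N=210). With X·W in the model the rate is about 5% throughout. With no true X·W effect it is about 5% either way.

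**5. Binary Study 1 outcome.** Logistic simulation, N=150, *a* from .26 to .39. Assumed: aggression near 20% or 40%, log-odds of .5 per SD of mediator and .4 for condition. M·W is significant in about 7–11% of trials at an X·W odds ratio of 2 per SD of moderator, 9–18% at 3 and 12–26% at 4, against about 5% with X·W included.

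**6. The SAP's safeguards**
- *Scheffé.* The family is not defined. If it held two contrasts, the critical value at N=150 would be √(2 × 3.06) = 2.47, for which an unbiased single test has size about 1.5%. At f²=.053 and a=.316–.39 the rate would be about 6.5–9%. With four contrasts it would be about 2%. The rate falls, but the displaced coefficient a·c does not.
- *The 1% variance rule.* At N=150, p<.05 needs a partial f² of about 1.976²/145 = .027. If the model explains 22% of variance (the SAP's figure for alcohol and objectification together), that is .027 × .78 = 2.1% of total variance, so a significant term passes.

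**The case against.** The strongest reply is that the protocol names no path, and the SAP supplies the detail. It states path-level hypotheses for Aim 3 and fits terms that match them. If condition moves the mediator and the moderator changes the mediator's effect, the indirect effect of alcohol varies with the moderator. This stands: a reader might infer that the protocol's prediction goes wholly untested, and the documents do not support that. What remains untested is moderation of the total and direct effects and of the condition effects on the mediators. The SAP is dated 5-10-19 and the protocol 2-28-20, so the SAP cannot be taken to have superseded the protocol's broader statement.

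A second reply is that the misattribution is conditional. It needs a true condition × moderator effect and a condition effect on the mediator; the figures also set mediator × moderator to zero, contrary to the SAP's hypotheses. This also stands, although the study predicts the first two. Even then the moderator is real, and the error lies in the path credited.

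A third is that linear rates overstate the problem for Study 1 aggression, which is a single binary choice, and that uncorrected rates are not those of the written plan. Both points are right. Larger rates follow from a larger interaction such as f²=.10, but nothing in the documents supports that value, and the SAP itself stresses that interactions explain little variance.

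**Conclusion.** The concern holds in a limited form. The protocol's Aim 3 prediction about the randomised conditions is tested only implicitly, through the indirect effect. The total, direct and condition-to-mediator parts have no test. If the predicted condition × moderator effects exist, part of them will be credited to mediator paths. For a linear outcome (Study 2 and the objectification equations) this raises a nominal 5% to about 8–13% for a small interaction and to about 11–22% at the SAP's detectable sizes. For binary aggression the rise is slight at an odds ratio of 2 and substantial only at 3 to 4. These rates rest on *a* between .26 and .39, a true mediator × moderator effect of zero, and two-sided .05 before correction. A Scheffé correction lowers them without removing the misattribution. It does not follow that a significant mediator × moderator result would be false; without the extra term it cannot be separated from moderation of the condition effect. This is a cheap improvement and does not invalidate the plan.

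**What to change.** In the SAP's Aim 3 paragraphs:

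1. Add condition × baseline-moderator terms (alcohol in Study 1; alcohol and gaze in Study 2) to the H1a/H2a and H1b/H2b regressions. Name them as the direct test of the protocol's prediction and place them in the same, defined multiplicity family.
2. Keep those terms in every model that contains mediator × moderator, and describe the mediator terms as mechanistic.

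If only the mediator paths are intended, narrow the protocol's Aim 3 prediction to them instead.

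No new data are needed, but three costs should be stated:
- **More tests:** with four moderators, 4 × 1 = 4 per outcome in Study 1 and 4 × 2 = 8 in Study 2.
- **Power for mediator × moderator:** at f²=.053 and N=150 it falls from about .76 to .68–.73.
- **Power for condition × moderator on binary aggression:** only about 30–50% at an odds ratio of 2 per SD, so a null result there should not be read as absence of moderation.

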Cover Page

Type of Document: Study Protocol

Official Title of the study: Integrating Alcohol Myopia and Objectification to Understand Sexual Assault

NCT number: NCT03956238

Date of document: 2-28-20

Study 1: Sexual Objectification and Alcohol-Involved Sexual Aggression (Aim 1)

Participants and procedures. Study 1 will utilize a mixed model experimental design with intoxication (alcohol, placebo control) as the between-participants factor and eye tracking and implicit association tests used to assess objectification as within-participants factors. We expect the behavioral manifestations of myopia—impaired attention and sexual objectification— will emerge in the intoxication condition compared to the placebo control condition. Specifically, community men (n = 150) will come to the lab for a study on “alcohol and perceptions” and be randomized to consume a moderate-dose alcohol or placebo drink, after which they will complete the attention, objectification, and sexual aggression measures.

Alcohol administration. Standard alcohol administration procedures used by the PIs in prior studies (e.g., Watkins, DiLillo, & Maldonado, 2015) will be employed. Men in the alcohol condition will be administered a dose of .90 g(amount of alcohol)/kg(men’s weight) of 95% alcohol U.S. Pharmacopoeia (USP) mixed at a 1:5 ratio with a mixer to achieve a target BAC of at least .08%. Four milliliters of alcohol will be added to the mixer and alcohol will be sprayed on the rim of placebo beverages. All participants will have up to 30 minutes for beverage consumption. For participants in the alcohol condition this will be followed by a 20-minute absorption period. Because the effectiveness of alcohol placebo manipulations tends to diminish starting at about 30 minutes after beverage consumption (Bradlyn & Young, 1983), participants in the placebo condition will have a shorter, 10-minute absorption period.

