Cover Page

Type of Document: Statistical Analysis Plan

Official Title of the study: Integrating Alcohol Myopia and Objectification to Understand Sexual Assault

NCT number: Not yet assigned

Date of document: 5-10-19

Statistical Analysis Plan

All analyses for Study 1 and 2 will be conducted using Mplus v. 7.4 (Muthén & Muthén, 2015), except descriptive statistics and multivariate analysis of variance models to investigate participant differences between intoxication condition groups (i.e., alcohol, placebo control), as well as order effects and repeated measures effects for the Eye-Tracking Objectification Task and the Implicit Association Task, will be examined using SAS v. 9.4 (SAS Institute, 2014). Manipulation checks will be assessed prior to analyses and appropriate controls (e.g., key demographics such as sexual orientation, race/ethnicity) will be included in the models. Study 1 tests the hypotheses for Aim 1 that intoxication causes more aggression in men (H1a), more impaired attention and objectification (H1b), that impaired attention and objectification mediate the relation between alcohol and aggression (H1c). Hypothesis 1a will be tested by regressing the measures of sexual aggression on intoxication (alcohol vs. placebo control) groups. Hypothesis 1b will be tested by regressing the measures of impaired attention and objectification separately on intoxication condition. Hypothesis 1c will be tested by simultaneously regressing the impaired attention measures on intoxication condition, the objectification measures on the impaired attention measures and intoxication condition, and the aggression measure on the impaired attention, objectification, and intoxication condition measures. The mediated effect of intoxication condition on aggression through each measure of impaired attention and of objectification, as well as the overall mediated effect through all measures, will be estimated using the MODEL INDIRECT statement in Mplus. Mediation will be tested using the bias-corrected bootstrap test (1,000 samples, MacKinnon, 2008).

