Study 2 tests the hypotheses for Aim 2 that intoxication condition (i.e., alcohol, placebo control) and objectification condition (i.e., objectifying gazes, eye contact control) each independently cause more victimization risk in women (H2a) and that these two factors interact; the highest victimization risk will occur in women who consumed alcohol and were sexually objectified. Likewise, intoxication and sexual objectification will interact to cause more impaired attention and self-objectification (H2b) with the higher levels occurring for the women who consumed alcohol and were sexually objectified than for women in the other experimental conditions. Finally, Study 2 tests whether impaired attention and self-objectification mediate the relation between alcohol, sexual objectification, and victimization risk (H2c). Hypotheses 2a-c will be tested in the same manner as Hypotheses 1a-c but with alcohol condition, objectification condition, and the interaction between these factors as predictors in the regression, the objectification measures replaced with self-objectification measures, and the aggression measure replaced with the victimization risk perception measure. Alternative models also will be tested. For example, in Study 2, separate indirect paths for both attention and self-objectification between alcohol and sexual victimization risk will be included, assessing whether self-objectification adds explanatory value beyond impaired attention and vice versa. In addition, mediation can be tested independently for each of the four experimental condition groups (e.g., alcohol-objectifying gazes) to determine if the same mechanisms are working for each group.

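### For the separately fitted Aim 3 interactions, the Scheffe correction controls Type I error but is needlessly strict; Holm's method fits these tests and keeps more power

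*SAP*

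**What the plan says.** The SAP builds the Aim 3 models from the mediation models of Aims 1 and 2 by "adding the two-way interactions between measures of myopia (impaired attentional capacity and sexual and self-objectification) and the moderators". Testing has two stages. Because the moderators are correlated, "the two-way interactions will be examined individually first". Then "All significant interactions will be added to the model simultaneously to examine whether moderation remains".

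The only provision for multiplicity follows directly: "Type I error inflation across models will be controlled for using the Scheffe correction". The same sentence adds that effects below 1% of total variance will not count as important, "regardless of statistical significance". The SAP does not state the family of tests, its size, the Scheffe degrees of freedom or alpha.

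The hypotheses in that paragraph concern two kinds of interaction. Chronic objectification (or self-objectification) is to moderate the path from impaired attention to situational objectification. Assault history, sex-related alcohol expectancies and rape myth acceptance are each to moderate the path from objectification to aggression or victimization risk.

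**The concern.** Scheffe's critical value comes from one model's F distribution and protects every linear combination of that model's parameters. Here each interaction is a one-degree-of-freedom term in its own model. The outcomes differ: several objectification measures, and in Study 1 a yes/no measure of aggression. No single F statistic spans these models, so the analyst must choose a dimension for the correction.

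The natural choice is the number of interactions. The threshold then also pays for protecting arbitrary combinations of interactions, which nobody plans to test. The SAP's Statistical power section itself remarks that interactions explain little variance compared with main effects, so a threshold stricter than necessary is costly for this aim in particular. The choice decides which moderators go forward to the simultaneous model and are reported as significant.

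**Working it through.** **Inputs**

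- Study 1: N = 150, power .80, f² = .053, four predictors (SAP, Statistical power). Residual df = 150 − 4 − 1 = 145.
- Alpha is not stated. I assume .05 for a one-df F test (two-sided).
- Family size m is not stated, so it is varied. The Protocol's Study 1 Objectification section gives three measures (eye tracking, B-IAT, questionnaire); there is one attention scale.
  - Hypothesised terms: attention × chronic objectification on 3 measures, plus 3 measures × 3 moderators on aggression: 3 + 9 = 12.
  - Each objectification measure as its own family: 1 + 3 = 4, or 3 if only its moderators of the aggression path are counted.
  - Every myopia measure × every moderator: 4 × 4 = 16.

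**Step 1: the SAP's own figure.** With a noncentral F test, df1 = 1, df2 = 145 and λ = f² × N = .053 × 150 = 7.95, power at alpha .05 is .80 (.7998). The figure reproduces with no correction applied.

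**Step 2: thresholds and power, Study 1**

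- Set-wise Scheffe: reject if F > m × F(.95; m, 145). For m = 12 this is 12 × 1.8195 = 21.83, so critical |t| = √21.83 = 4.67.
- Holm's first and strictest step: reject if F > F(1 − .05/m; 1, 145). For m = 12 this is 8.48, so critical |t| = 2.91.

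| m | Scheffe F | Holm first-step F | Per-test p under Scheffe | Power, Scheffe | Power, Holm first step |
|---|---|---|---|---|---|
| 3 | 8.00 | 5.87 | .0053 | .50 | .65 |
| 4 | 9.74 | 6.40 | .0022 | .39 | .61 |
| 9 | 17.50 | 7.92 | .00005 | .09 | .50 |
| 12 | 21.83 | 8.48 | .000007 | .04 | .47 |
| 16 | 27.42 | 9.03 | .0000006 | .01 | .43 |

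The last column is a floor for Holm, whose later steps are easier. In a simulation of 12 independent tests (40,000 runs), Holm's average power was .47 to .57, depending on how many interactions were real. Scheffe stayed at .04.

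**Step 3: what the strictness means at m = 12.** A term needs a partial R² of 21.83 / (21.83 + 145) = 13% to be declared significant. The effect needed for .80 power is f² = .204 under Scheffe and .094 at Holm's first step. With 12 independent tests, familywise error under Scheffe is about .00008, against the .05 it could use.

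**Step 4: Study 2.** N = 210, f² = .044, seven predictors, df2 = 202. A one-df test gives unadjusted power .857, not the stated .80; that mismatch is a separate matter. At m = 12, power is .06 under set-wise Scheffe and .56 at Holm's first step. At m = 4 it is .47 against .70.

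**Step 5: the groups-minus-one computation.** Study 1 is designed "with intoxication (alcohol, placebo control) as the between-participants factor", so there are two groups. The multiplier is 1 and the threshold is 1 × F(.95; 1, 148) = 3.905, which is the unadjusted value. In Study 2, four cells give 3 × F(.95; 3, 206) = 7.95, a per-test p of .0053. Power at f² = .044 is then .59, and familywise error for 12 independent tests is 1 − (1 − .0053)^12 = 6.2%.

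**The case against.** **Scheffe is conservative, so the promise to control Type I error is kept.** On the set-wise reading this stands. At every m computed the threshold lies above Bonferroni's, so familywise error is controlled whatever the dependence between tests. The defect is lost power, not invalidity.

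**The size of the loss depends on a family the SAP never defines, and on f² = .053, which is a sensitivity limit and not an expected effect.** This also stands. With 3 or 4 tests the loss is real but moderate. At f² = .10 and m = 4, Scheffe's power is .77. At m = 12 it is .22 against .83 for Holm's first step, so the criticism survives for larger effects if the family is large. The direction is the same at every size from 3 to 16.

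**Nine of the 12 counted Study 1 terms predict a dichotomous outcome.** For those the F-based figures are approximate. The SAP's own sensitivity analysis uses the same approximation.

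**A reader might infer that Study 1 has no correction at all**, because two groups give a multiplier of 1. The text does not support this as the main reading: the hypothesised interactions pair myopia measures with moderators, and randomised group appears in none of them. In Study 2 a four-cell computation would come out close to Holm for 12 tests (power .59 against .56), though only by coincidence, since that threshold does not depend on the number of interactions.

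**A reader might also infer that Scheffe is meant to cover the Aim 1 and 2 regressions and the bootstrap mediation tests.** The sentence closes the Aim 3 paragraph, and nothing in the SAP's text on Aims 1 and 2 refers to it. Extending Holm to those tests would be new policy, and 1,000 bootstrap samples would serve it poorly.

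**Conclusion.** The point holds for the Aim 3 interactions. Scheffe does not match separate one-df tests with different outcomes. Applied in the natural way, it controls familywise error at an unnecessary cost in power: at the SAP's own Study 1 effect, .15 with 3 tests (.65 − .50), about .23 with 4 (.615 − .386) and .43 with 12 (.47 − .04). This assumes alpha of .05 and a family size the SAP does not give, and it is approximate for aggression. The ranking of the two methods does not depend on the family size over the range checked; the size of the gap does.

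The documents do not support saying that the correction is invalid, that Study 1 is certainly left uncorrected, or that moderators are almost undetectable whatever the family.

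**What to change.** Replace the Scheffe part of the sentence with:

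*Within each study, familywise error for the hypothesised Aim 3 interactions (listed by measure and moderator) is controlled at .05 by Holm's method at the individual-interaction stage. The simultaneous model is a follow-up of the interactions so retained. Other interactions are exploratory.*

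The list must be written out, because the SAP does not give it and the count of 12 used here is an inference. Holm needs only p-values, so it works for linear and dichotomous-outcome models alike, and it is valid under any dependence. The 1% importance floor can stay. The sensitivity figures in the Statistical power section should be restated at the adjusted level, since the Study 1 figure corresponds to an unadjusted test.

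The cost is one sentence, the list, and a ranking of p-values the analysis already produces; no design change or new data is needed. There is one downside: if Scheffe would have been computed from the number of groups, some nominally significant Study 1 interactions would no longer count.
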